13.3 Treatments

This is a single arm study with the intervention arm receiving 81 mg aspirin daily during the primary neoadjuvant chemotherapy treatment course.

13.4 Primary Objective

Refer to Section 6 for the primary objective and endpoint. In brief, the primary objectives of this study are to determine the efficacy and safety of low dose aspirin for the prevention of VTE among women receiving neoadjuvant chemotherapy for advanced ovarian cancer.

8.4.

8.7.1. Variable

The study variable is whether or not women receive aspirin thromboprophylaxis during neoadjuvant chemotherapy.

8.7.2. Statistical Hypothesis, Model, and Method of Analysis

The goal for initiating accrual into this study will be September 1st, 2020. Patients will continue to be enrolled through December 30th, 2021. Subjects will be followed through the primary NACT treatment course until interval debulking surgery, with an estimated duration of 6-9 months following enrollment depending on the number of NACT cycles the individual undergoes. The primary efficacy outcome of this study is rate of VTE among the study cohort during NACT. The primary safety outcome is the incidence of clinically significant adverse drug events. Data from medication adherence diaries and AE symptom questionnaires will be reviewed and entered into the REDCap database. An intention-to-treat analysis will be performed. Subjects withdrawn due to medication intolerance or adverse drug events will be censored, and the research team will continue to collect clinical data for the predetermined follow up period.

We will calculate the incidence of VTE during the study period defined above (enrollment to interval debulking surgery or 1 week after completion of the primary neoadjuvant chemotherapy course if debulking surgery is deferred) and estimate a 95% exact binomial confidence interval. Since this is a pilot study, the incidence of venous thromboembolism in the study population will be compared to a historical control from a previous research study

of the incidence of venous thromboembolism among women receiving neoadjuvant chemotherapy for advanced ovarian cancer in which the majority of patients were from Duke. A drop greater than 20% (from approximately 8% to 6.4%) in the rate of venous thromboembolism would be considered clinically meaningful. If the true VTE rate is 6.4%, the width of the 95% exact binomial confidence interval will be 0.098. We will also monitor for adverse safety events related to low dose aspirin use, including major or minor bleeding events, gastrointestinal complications, and medication intolerance (side effects or adverse reaction). Further detail regarding AE monitoring and reporting is outlined in a previous section.

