3.3 Design and Procedure

Subjects with advanced EOC (including primaries of ovarian, Mullerian, fallopian tube, or peritoneal origin) will be screened for eligibility at Duke Gynecology Oncology clinic visits prior to initiation of NACT. Selection criteria are detailed in a subsequent section. Once determined eligible, a provider will approach the patient and inquire about interest in participating in the study. If the patient desires to receive more information, clinical research personnel will discuss the study with patient and obtain informed consent if all selection criteria are met (detailed in a subsequent section). If the research team is unable to meet with a patient face to face but the patient is interested in participating, the same process will be facilitated via telephone once secure identifiers are met. If the patient consents, they will then be considered an enrolled study subject. Electronic consent will be performed in REDcap. Following enrollment, basic demographic information for each patient will be recorded in a secure REDCap database. Specific demographic data and security concerns are further outlined in a later section.

Patients will be enrolled and will receive aspirin at the Macon Pond location. All study activities will be performed by the study coordinators, so we do not anticipate needing assistance from the Duke Raleigh study team.

The primary selection criterion is a Khorana score of 1; additional criteria are detailed in a subsequent section. The Khorana score will be calculated according to the following parameters in closest proximity to the first cycle of chemotherapy: 1 point for gynecologic cancer, 1 point for BMI ≥ 35 , 1 point for Hgb < 10 or use of red blood cell growth factors, 1 point for leukocyte count $> 11,000$, and 1 point for platelets $\geq 350,000$. Patients therefore have a baseline Khorana score of 1 and are ineligible if any additional Khorana score parameters are met. Prior to the April 2021 amendment, Khorana score was not a part of the inclusion criteria. Any existing patient with a Khorana score of more than 1 who is receiving study drug at the time the amendment is approved will be contacted by the study PI to discuss switching to a DOAC. The patient will have the option to remain on study and complete their aspirin regimen or come off study and begin a

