DOAC instead. Any existing patients with a Khorana score of more than 1 who have already completed their aspirin regimen and are considered "on follow up" will remain on study.

Once enrolled in the study, subjects will receive a 30-day supply of low dose aspirin from a study team member and will be instructed to start taking one 81 mg tablet daily starting the first day of their first neoadjuvant chemotherapy cycle. Subjects may also be consented after the first day of their first cycle so long as they are taking the aspirin by the end of the day of their second cycle. Patients who are already on low dose aspirin for another indication will still be eligible for the study but will be instructed to take the study drug such that adherence can be monitored. These patients will continue their prior regimen following completion of NACT. Participants will be instructed to complete medication adherence diaries and AE symptom questionnaires. At each subsequent clinic visit for consideration of an additional NACT cycle, a member of the research team will review medication adherence diaries and AE symptom questionnaires and administer the Voils DOSE-Nonadherence measure survey. If symptoms are concerning for a potential AE, the research team personnel will inquire further and discuss with the PI. Please see subsequent sections related to AE monitoring and reporting. No additional components of history and physical exam will be completed outside standard of care performed by the patient's provider prior to initiation of an additional cycle of NACT. Different patients may undergo different numbers of NACT cycles, and thus the 30-day supply of aspirin will be refilled by a member of the research team when the decision is made to proceed with an additional cycle.

Participants who experience clinically significant adverse drug events such as bleeding or medication intolerance will be withdrawn from the study. Subjects with significant chemotherapy-induced thrombocytopenia (platelet count less than 50,000) will be instructed to stop taking daily aspirin for 1 week until platelet counts normalize. If a subject withdraws from the study voluntarily, there will be no further follow up. If a participant is censored due to development of a VTE or clinically significant AE, the research team will continue to collect clinical data until the end of the predetermined follow up period.

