6 OBJECTIVES AND ENDPOINTS

	Objective	Endpoint	Analysis
Primary	To determine the efficacy of low dose aspirin for the reduction of venous thromboembolism among women receiving neoadjuvant chemotherapy for advanced ovarian cancer.	Incidence of venous thromboembolism during neoadjuvant chemotherapy.	See Section 13.4
Other Primary	To determine safety and medication adherence with the use of low dose aspirin for the reduction of venous thromboembolism among women receiving neoadjuvant chemotherapy for advanced ovarian cancer.	Incidence of clinically significant adverse drug events. Rate of medication nonadherence.	See Section 13.4

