7 INVESTIGATIONAL PLAN

7.1 Study Design

This is a single-arm, single-center, interventional pilot study to determine the efficacy and safety of low dose aspirin for the prevention of VTE among women receiving NACT for advanced ovarian cancer when compared with a historical control.

Eligible participants will be recruited from patients with advanced epithelial ovarian cancer (including primaries of ovarian, Mullerian, fallopian tube, or peritoneal origin) who are initiating NACT at the Duke Gynecology Oncology clinics at the Duke Cancer Center and Macon Pond location (Duke Women's Cancer Care Raleigh) or Sarasota Memorial Healthcare System. A provider will approach the patient and inquire about interest in participating in the study. If the patient desires to receive more information, clinical research personnel will discuss the study with the patient and obtain informed consent if all selection criteria are met (detailed in a prior section). If the patient consents, they will then be considered an enrolled study subject. Electronic consent will be performed in REDcap. Following enrollment in the study, basic demographic information for each patient will be recorded in a secure REDCap database. The initial medical history and physical examination will be conducted per standard of care by the patient's provider at the clinic visit. Patients will be enrolled and will receive aspirin at the Macon Pond location. All study activities will be performed by the study coordinators, so we do not anticipate needing assistance from the Duke Raleigh study team.

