Once enrolled in the study, subjects will receive a 30-day supply of low dose aspirin from the research team and will be instructed to start taking one 81 mg tablet daily starting the first day of their first NACT cycle. Subjects may also be consented after the first day of their first cycle so long as they are taking the aspirin by the end of the day of their second cycle. Subjects will continue taking aspirin until the day of their interval debulking surgery. Patients who are already on low dose aspirin for another indication will still be eligible for the study but will be instructed to take the study drug such that adherence can be monitored. These patients will continue their prior regimen following completion of NACT. Patients will be instructed to complete medication adherence diaries and AE symptom questionnaires. At each subsequent clinic visit for consideration of an additional NACT cycle, a member of the research team will review medication adherence diaries and AE symptom questionnaires. Patients will also be instructed to complete Voils DOSE-Nonadherence measures at each visit. If symptoms are concerning for a potential AE, the research team personnel will inquire further and discuss with the PI. Please see subsequent sections related to AE monitoring and reporting. No additional components of history and physical exam will be completed outside standard of

care performed by the patient's provider prior to initiation of an additional cycle of NACT. Different patients may receive different numbers of cycles, and thus the 30-day supply of aspirin will be re-filled when the decision is made to proceed with an additional cycle.

This study will not impact standard of care treatment. The incidence of VTE will be calculated from the study population and compared with a historical control from a similar population cohort. The incidence of adverse drug events will also be monitored and reported as detailed in a subsequent section.

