10.4 Follow-up Period

Patients will be followed from initiation of NACT through interval debulking surgery without any additional follow up period.

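### The plan gives conflicting start dates for counting VTE (consent or start of NACT), so pre-chemotherapy clots may enter the primary rate and some early NACT time is left out

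*Combined protocol and SAP*

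**What the plan says.** The documents give several starting points for the same outcome.

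- **Enrolment.** The analysis section (printed 8.7.2, listed as 13.4.2 in the contents) says: "We will calculate the incidence of VTE during the study period defined above (enrollment to interval debulking surgery". Section 3.6 repeats the rule, and Section 3.5 starts participation at enrolment.
- **During or from NACT.** Section 6 gives the endpoint as "Incidence of venous thromboembolism during neoadjuvant chemotherapy". The analysis section itself says: "The primary efficacy outcome of this study is rate of VTE among the study cohort during NACT". Section 10.4 says: "Patients will be followed from initiation of NACT through interval debulking surgery without any additional follow up period".
- **Both at once.** The introduction to Section 10 names the start of NACT and enrolment together as one starting point for follow-up.

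These are different dates. Section 7.1 says: "If the patient consents, they will then be considered an enrolled study subject". Section 3.3 says that subjects "will be screened for eligibility at Duke Gynecology Oncology clinic visits prior to initiation of NACT", and the schedule in Section 10 puts consent in a screening column before cycle 1. Subjects "will be instructed to start taking one 81 mg tablet daily starting the first day of their first NACT cycle" (Section 7.1). Sections 3.3, 7.1 and 10 also allow consent after that day, provided aspirin is being taken by the end of the day of cycle 2.

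The section on missing values (printed 8.7.3) applies intention to treat to all enrolled subjects. Section 7.4 defines evaluable subjects as those given aspirin and receiving NACT, but Section 13 does not use that term.

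**The concern.** There is no control arm, so the efficacy objective rests on comparing the observed rate with a historical rate of about 8%. Sections 3.2, 5.1 and 5.3 describe that rate as VTE in women receiving NACT, or during NACT. If the trial rate also contains clots found after consent but before any chemotherapy or aspirin, it covers a period that the benchmark is not described as covering. Conversely, if counting starts at consent for a woman already in NACT, the trial rate omits part of the period that the benchmark is described as covering. Expected counts are small, so one or two events classified differently can change how the result reads against the 6.4% mark.

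**Working it through.** **1. The plan's own figure.** Planned N is 60 + 60 = 120 (Section 7.1). At 6.4%, 120 × 0.064 = 7.68 events, rounded to 8. The exact 95% interval for 8/120 is 2.92% to 12.71%, a width of 0.0979. This reproduces the stated 0.098. At N = 60 (4/60) the width is 0.1435, so the plan's figure rests on 120.

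**2. The contrast of interest.** 120 × 0.08 = 9.6 and 120 × 0.064 = 7.68, a difference of 1.92 events. One event is 1/120 = 0.83 percentage points, or 0.83/1.6 = 52% of the drop from 8% to 6.4%. An observed 7/120 is 5.8%; 8/120 is 6.7%.

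**3. Two women traced through the text.**

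- *Woman A* consents before NACT and has a clot diagnosed before cycle 1. Under the enrolment window and the all-enrolled set she is an event. Under Section 6, Section 10.4 and the outcome sentence of 8.7.2 she is not. If she never receives aspirin or NACT she is not evaluable under Section 7.4, but the analysis does not invoke that definition. No rule reports her separately.
- *Woman B* consents after cycle 1 day 1. The enrolment window omits the NACT time before her consent. A window from the start of NACT includes it, but she had to be eligible at consent. Section 9.2 excludes women already on anticoagulation, so a clot treated that way in the interval would have kept her out. Her earlier NACT time is event-free by selection.

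**4. Size of the lead-in for women like A.** Expected extra events = N × p × g / T, with N = 120, p = 0.08, g the gap in weeks from consent to cycle 1, and T the duration in weeks. T comes from the documents: about 6 months (Section 3.5) and 6 to 9 months (Sections 3.6 and 8.7.2), taken as 26 to 39 weeks. The gap is not given; 0 to 3 weeks is an assumption, applied to every woman.

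| g (weeks) | T = 39 | T = 26 |
|---|---|---|
| 0 | 0 | 0 |
| 1 | 9.6 × 1/39 = 0.25 | 9.6 × 1/26 = 0.37 |
| 3 | 9.6 × 3/39 = 0.74 | 9.6 × 3/26 = 1.11 |

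For gaps of 1 to 3 weeks, the range of 0.25 to 1.11 events is 0.21 to 0.92 percentage points (divide by 120). A true 6.4% would be observed as about 6.6% to 7.3%.

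**5. Size of the opposite effect for women like B.** As an extreme, let every woman miss the first 3 weeks of NACT (an assumption; cycle length is not stated). With even risk and no drug effect, 8% would be observed as 8% × (1 − 3/39) = 7.4% or 8% × (1 − 3/26) = 7.1%. This is an upper bound, since only some women enter late.

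**6. Net effect.** No woman can be both A and B, and the documents give neither the mix nor the gaps. The sign of the net bias cannot be derived.

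**The case against.** Counting from enrolment is a normal intention-to-treat convention, and the plan specifies no formal test. A shift of 0.2 to 0.9 points is small beside an interval nearly 10 points wide. If consent is usually taken at or close to cycle 1, the lead-in is negligible. The even-risk calculation also applies the NACT-period hazard to time before chemotherapy, for which the documents give no rate. Finally, the documents never say when the historical study began counting, so the mismatch is with how the 8% is described, not with a known start date.

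All of this limits the size. It does not remove the contradiction. In a randomised trial both arms share the lead-in; here the comparator is not described as having one.

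Three stronger readings are tempting.

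- *A reader might infer that pre-aspirin clots are definitely scored as aspirin failures and that the rate is therefore biased against aspirin.* That scoring follows from one of several conflicting statements, and late consent pulls the other way.
- *A reader might infer that aspirin always starts on cycle 1 day 1.* The late-consent route allows a start as late as cycle 2.
- *A reader who assumes a 13-week course gets up to 9.6 × 3/13 = 2.2 lead-in events and might conclude that they would cancel the whole contrast.* The documents' own durations are 26 to 39 weeks, which give at most about 1.1 under the same gap.

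**Conclusion.** The concern holds as an unreconciled start date for the primary endpoint. The window in Sections 3.6 and 8.7.2 is wider than the stated endpoint for women who consent before NACT and narrower for women who consent after cycle 1 day 1. The first effect is about 0.25 to 1.1 events at N = 120 if risk is even over 26 to 39 weeks and every woman has an assumed 1 to 3 week gap; it is near zero if consent falls close to cycle 1. That compares with a contrast of 1.92 events. The second effect has the opposite sign and also cannot be sized from the documents. The documents support neither a net direction nor a claim that the target effect would be hidden. They do support settling the rule before analysis, because a single reclassified event is worth half the target drop.

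**What to change.** In Sections 3.6 and 8.7.2 (13.4.2), start the primary VTE window at day 1 of cycle 1 for women consented on or before that day, in line with Sections 6 and 10.4. Reconcile Section 3.5 and the introduction to Section 10 with this, and state the resulting primary denominator in 8.7.3 (13.4.3).

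- List VTE between consent and cycle 1 day 1 separately, and give the all-enrolled rate from consent as a sensitivity result.
- For women consented after cycle 1 day 1, count from consent, and show the rate with and without them.
- State the start date used for the historical rate.

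Do not start the window at the first study tablet. That would drop early-NACT events in women who start aspirin late and so favour aspirin. It would not match Sections 6 and 10.4, and it could not be applied to a historical cohort that had no study tablet.

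The cost is wording. The rule needs the dates of consent, cycle 1 day 1 and VTE diagnosis, with no new visits or procedures. The small downside is that a few women with a pre-NACT VTE leave the primary denominator; the separate listing and the sensitivity result keep them visible.

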3.2 Background and Significance

VTE is a known potential complication of malignancy and is particularly common among women with epithelial ovarian cancer (EOC).^[1,2] In addition to having active cancer, women with EOC are predisposed to other well-established risk factors for VTE, including impaired mobility, increasing age, and advanced disease.^[3] The risk of VTE is even greater among patients with clear cell histology, thrombocytosis, high grade tumors, and co-morbid cardiovascular risk factors (e.g., obesity, hypertension, diabetes).^[4-7] In a recent study at our institution, we found that women with advanced ovarian cancer receiving NACT are at high risk for VTE with an incidence of nearly 8%.^[8]

Importantly, the occurrence of VTE among patients with EOC is associated with increased morbidity, decreased survival, and increased healthcare costs.^[9-11] Timely interval debulking surgery and the ability to achieve of optimal surgical debulking also remain critical components of care for advanced EOC. In the aforementioned study, we observed that the average time from start of NACT to interval debulking surgery was longer for patients who experienced a VTE during NACT as compared to those who had not; these patients were also less likely to have their disease optimally debulked at the time of interval surgery. The high incidence of VTE during NACT reported in our study as well as the associated morbidity contributes to a growing body of evidence suggesting that thromboprophylaxis during NACT is warranted.

According to the current guidelines from the American Society of Clinical Oncology, thromboprophylaxis with either apixaban, rivaroxaban, or low molecular weight heparin (LMWH) is recommended for high risk ambulatory cancer patients (defined as a Khorana score greater than or equal to 2) receiving systemic chemotherapy. Patients with a primary gynecologic malignancy receive one point in the Khorana score at baseline, and the majority of ovarian cancer patients would meet criteria for an additional point. High risk Khorana scores defined as 3 or greater have a 6.7-7.1% risk of VTE which is similar to the incidence defined in the previously described study of patients receiving NACT for advanced EOC. These patients are therefore considered high risk for adverse thromboembolic events when initiating systemic chemotherapy.

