Considering the above recommended agents, our recent institutional data (unpublished) demonstrated that apixaban is not a cost-effective strategy among women with ovarian cancer receiving NACT specifically, and insurance coverage of apixaban and other direct oral anticoagulants is not yet well established. A query of medical oncologists affiliated with the Duke Cancer Institute revealed that the majority of providers are generally not initiating direct oral anticoagulants despite the above guidelines. LMWH, another alternative injectable agent, is expensive and poorly tolerated by patients for prolonged periods of time due to its route of administration.

Low dose aspirin, in contrast, is an oral agent and performed better than apixaban in our cost effectiveness analyses even when potential bleeding rates were upwardly adjusted. It is also already used off-label for a broad range of clinical indications, including as an acceptable alternative for thromboprophylaxis among patients with multiple myeloma receiving antiangiogenesis agents with chemotherapy and/or dexamethasone as well as for postoperative prophylaxis after select orthopedic procedures. We therefore hypothesized that low dose aspirin would be a safe and effective method of thromboprophylaxis for women with advanced ovarian cancer receiving NACT.

The above ASCO guidelines were subsequently endorsed by the Society for Gynecologic Oncology in January 2021. Thus initiation of thromboprophylaxis with apixaban, rivaroxaban, or LMWH is recommended for high risk ambulatory gynecologic cancer patients receiving chemotherapy with a Khorana score ≥ 2 . Interim analysis of the initial 10 recruited patients demonstrated 3 VTE events. The division of Gynecologic Oncology at Duke subsequently endorsed the new guidelines. However, patients receiving NACT with a KS equal to 1 may also be at risk of a VTE given the high incidence previously documented, and although not candidates for DOAC therapy, may potentially benefit from initiation of low dose aspirin.

References listed in Section 15

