4 STUDY SCHEMA

5 BACKGROUND AND SIGNIFICANCE

5.1 Study Condition

In a recent study at our institution, we found that women with advanced ovarian cancer (including primaries of ovarian, Mullerian, fallopian tube, or peritoneal origin) receiving neoadjuvant chemotherapy (NACT) are at high risk for VTE with an incidence of nearly 8%.^[8]

Importantly, the occurrence of VTE among patients with EOC is associated with increased morbidity, decreased survival, and increased healthcare costs.^[9-11] Timely interval debulking surgery and the ability to achieve of optimal surgical debulking also remain critical components of care for advanced EOC. In the aforementioned study, we observed that the average time from start of NACT to interval debulking surgery was longer for patients who experienced a VTE during NACT as compared to those who had not; these patients were also less likely to have their disease optimally debulked at the time of interval surgery. The high incidence of VTE during NACT reported in our study as well as the associated morbidity contributes to a growing body of evidence suggesting that thromboprophylaxis during NACT is warranted; there is currently no standard of care alternative for thromboprophylaxis during NACT.

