The primary selection criterion is a Khorana score of 1; additional criteria are detailed in a subsequent section. The Khorana score will be calculated according to the following parameters in closest proximity to the first cycle of chemotherapy: 1 point for gynecologic cancer, 1 point for BMI ≥ 35 , 1 point for Hgb < 10 or use of red blood cell growth factors, 1 point for leukocyte count $> 11,000$, and 1 point for platelets $\geq 350,000$. Patients therefore have a baseline Khorana score of 1 and are ineligible if any additional Khorana score parameters are met. Prior to the April 2021 amendment, Khorana score was not a part of the inclusion criteria. Any existing patient with a Khorana score of more than 1 who is receiving study drug at the time the amendment is approved will be contacted by the study PI to discuss switching to a DOAC. The patient will have the option to remain on study and complete their aspirin regimen or come off study and begin a DOAC instead. Any existing patients with a Khorana score of more than 1 who have already completed their aspirin regimen and are considered "on follow up" will remain on study.

An estimated 120 patients will receive neoadjuvant chemotherapy for advanced ovarian cancer at Duke Gynecology Oncology clinics for the designated study recruitment period of 09/01/2020 to 12/30/2021 with an estimated 50% accrual rate for a total of 60 enrolled patients. Sarasota Memorial Health Care System has been added as an additional site and plans to recruit an additional 60 subjects.

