13.6 Sample Size Calculation

Sample size calculation is not applicable to this study. Since this is a pilot investigation, the incidence of venous thromboembolism in the study population will be compared to a historical control from a previous research study of the incidence of venous thromboembolism among women receiving neoadjuvant chemotherapy for advanced ovarian cancer in which the majority of patients were from Duke. A drop greater than 20% (from approximately 8% to 6.4%) in the rate of venous thromboembolism would be considered clinically meaningful.

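### Eligibility is now Khorana score 1 only, but the efficacy comparison still uses an 8% / 6.4% benchmark from a cohort with no stated Khorana restriction and pools all enrolled patients

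*Combined protocol and SAP*

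**What the plan says.** - **Comparison.** Section 13.4.2 (printed as 8.7.2) states that "the incidence of venous thromboembolism in the study population will be compared to a historical control from a previous research study". Section 13.6 adds: "A drop greater than 20% (from approximately 8% to 6.4%) in the rate of venous thromboembolism would be considered clinically meaningful". Section 3.6 says the same.
- **Source of the 8%.** Section 5.1 reports that women with advanced ovarian cancer "receiving neoadjuvant chemotherapy (NACT) are at high risk for VTE with an incidence of nearly 8" percent. Neither Section 5.1 nor Section 3.2 mentions a Khorana restriction in that cohort or gives a rate by score.
- **Current eligibility.** Section 9.1 requires a Khorana score of 1. Section 7.1 explains that gynecologic cancer itself scores one point and that any further point makes a patient ineligible. It also records: "Prior to the April 2021 amendment, Khorana score was not a part of the inclusion criteria".
- **Score mix.** Sections 3.2 and 5.3 say that "the majority of ovarian cancer patients would meet criteria for an additional point".
- **Link to Khorana 1.** Section 3.2 says only that "patients receiving NACT with a KS equal to 1 may also be at risk of a VTE given the high incidence previously documented". No Khorana 1 rate is given.
- **Who is analysed.** Section 13.4.3 (printed as 8.7.3) specifies intention-to-treat for all enrolled subjects, and Section 13.1 defines a single analysis set. Section 3.3 keeps on study "Any existing patients with a Khorana score of more than 1 who have already completed their aspirin regimen". Those still on aspirin at the amendment could stay or leave for a direct oral anticoagulant. Section 13.2 lists Khorana score as a baseline characteristic only.
- **Early events.** Sections 3.2 and 5.3 report 3 VTE events in the first 10 patients.

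**The concern.** The amendment changed who can enter the trial but left the benchmark, the threshold and the analysis set as they were. There is no concurrent control, so the historical rate carries the whole efficacy inference.

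Two distortions act in opposite directions:

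- If Khorana 1 patients have a lower untreated risk than the historical cohort, their rate set against 8% looks like benefit even if aspirin does nothing.
- The early 3 of 10, carried into the pooled rate, pushes that rate up.

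The balance between the two depends on when the amendment took effect, not on the drug. Neither a rate below 6.4% nor a rate above it could be read as an aspirin effect in the population now being enrolled. The study has no formal test or go/no-go rule, so what is at stake is a misleading primary efficacy statement. Section 7.1 (under Safety Considerations) expects the results to inform the feasibility of larger studies.

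**Working it through.** **Inputs from the documents.** Benchmark 8% and threshold 6.4% (Sections 13.4.2, 13.6). Planned N = 60 + 60 = 120 (Section 7.1). First 10 patients: 3 events (Sections 3.2, 5.3). Stated width of the exact 95% interval at a 6.4% rate: 0.098 (Section 13.4.2).

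**Assumptions.** The documents give neither the share *s* of the historical cohort at Khorana 1 nor the risk ratio RR for Khorana ≥2 versus 1. I take *s* = 30–50%, in line with the statement that most ovarian cancer patients score higher, and vary RR. The one score-specific figure given, 6.7–7.1% at Khorana ≥3, does not supply a Khorana 1 rate.

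**1. The plan's own figure.** 0.064 × 120 = 7.68, rounded up to 8 events. The Clopper-Pearson interval for 8/120 is 2.92% to 12.71%, a width of 0.098. The figure reproduces and confirms that N = 120 is the working size.

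**2. Untreated Khorana 1 rate implied by 8% overall.** p1 = 0.08 / (s + (1 − s)·RR).

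| RR | s = 0.3 | s = 0.5 |
|---|---|---|
| 1.0 | 8.0% | 8.0% |
| 1.2 | 7.0% | 7.3% |
| 1.3 | 6.6% | 7.0% |
| 1.5 | 5.9% | 6.4% |
| 2.0 | 4.7% | 5.3% |

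Selection alone reaches 6.4% when s + (1 − s)·RR = 0.08/0.064 = 1.25, so RR = (1.25 − s)/(1 − s). This is 1.36 at s = 0.3, 1.42 at s = 0.4 and 1.50 at s = 0.5.

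**3. Chance of observing below 6.4% with inert aspirin.** Below 6.4% of 120 means at most 7 events. If 3 events come from the first 10, the other 110 may have at most 4 (3.6%). The first probability column is P(X ≤ 7) for Binomial(120, p), the second P(X ≤ 4) for Binomial(110, p). The expected pooled rate is (3 + 110p)/120.

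| Untreated rate p | 120 patients, all at p | 3/10 plus 110 at p | Expected pooled rate |
|---|---|---|---|
| 8% (no selection effect) | 25% | 5.5% | 9.8% |
| 6.4% | 50% | 16% | 8.4% |
| 5% | 75% | 35% | 7.1% |
| 4% | 89% | 55% | 6.2% |

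The 8% row is the reference: part of each probability is small-sample noise, and the change from that row is what selection adds. The expected pooled rate falls below 6.4% only if the other 110 run below (0.064 × 120 − 3)/110 = 4.25%.

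**4. Sensitivity to the early group.** The 10 + 110 split is an assumption; the number of pre-amendment patients is not given. If 10, 20 or 30 of the 110 are unrestricted patients at 8% and the rest are at 5%, the 35% becomes 31%, 26% or 23%.

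**5. Inert aspirin versus a real 20% reduction.** With an untreated rate of 5%, a true 20% reduction gives 4%. Falling below 6.4% then has probability 75% (inert) versus 89% (effective) in 120 Khorana 1 patients, and 35% versus 55% in the 3/10 plus 110 set. For an inert drug, patient mix moves the result from 75% to 35%. That exceeds the shift a real effect produces in either set (14 and 20 percentage points).

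**The case against.** The strongest counter-case is that this is an openly declared single-arm pilot with no sample size calculation, test or decision rule, and that every historical-control design confounds selection with treatment. The size of the bias rests on assumed inputs. At RR = 1 the benchmark is not biased, and at RR 1.2–1.3 the Khorana 1 rate is still 6.6–7.3%. The documents do not show a strong Khorana gradient among NACT patients: the unrestricted rate of nearly 8% is slightly above the 6.7–7.1% quoted for Khorana ≥3. The statement that most patients score higher concerns ovarian cancer patients generally, not the historical cohort. The exact interval for 7/120 is 2.4% to 11.6%, which covers both 8% and 6.4%, so the planned interval would itself warn against a conclusion.

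Much of this stands as a limit on magnitude. The size and direction are not known, the Khorana scores of the three early VTE cases are not stated, and imprecision is a separate weakness.

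It does not remove the defect. The compared populations differ on the very score used to select for VTE risk, and a specific amendment created that difference. Efficacy is a primary objective with a numeric threshold attached. A wide interval conveys sampling error; it does not tell the reader that the benchmark belongs to another population.

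Other provisions leave the pooled set less settled still. Higher-score patients may leave for a direct oral anticoagulant, Section 10.6 lists a Khorana score above 1 among reasons for withdrawal by the investigator, and Section 7.4 defines evaluable subjects differently from the all-enrolled set.

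**Conclusion.** The concern holds and should be fixed before analysis. As written, the only comparison serving the efficacy objective sets a mixture of unrestricted early patients and later Khorana 1 patients against an unrestricted cohort, and it cannot be attributed to aspirin in the population now enrolled.

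That conclusion rests on the text alone. The magnitudes are illustrations: they assume 8% overall in the historical cohort, 30–50% of it at Khorana 1, N = 120, and, for the pooled figures, 10 early patients with 3 events plus 110 others. On those assumptions a modest risk ratio of 1.36–1.50 would by itself bring the untreated Khorana 1 rate to the threshold, while the early events could hide a real reduction. The net direction cannot be determined from the documents.

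**What to change.** In Sections 13.4.2 and 13.6:

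1. Keep the all-enrolled VTE rate. Add VTE incidence with exact 95% intervals separately for baseline Khorana 1 and Khorana ≥2, and by enrolment before or after the amendment.
2. Compare each Khorana stratum with the same stratum's rate and exact interval in the historical data, and recompute the 20% threshold for Khorana 1 from that rate. For example, a 5% benchmark would give 4%, not 6.4%. Base the efficacy statement for the current target population on the Khorana 1 comparison, and state that this analysis was defined after the 10-patient look.
3. If the historical data cannot be split, state that the comparison with 8% / 6.4% is descriptive and supports no efficacy conclusion.
4. As a secondary correction, reconcile Section 13.5, which says no interim analysis is intended, with the 10-patient interim analysis reported in Sections 3.2 and 5.3.

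**Cost.** On the trial side this is analysis wording, since Khorana score is already a listed baseline variable. The historical side needs a re-tabulation using BMI, blood counts and the item "1 point for Hgb < 10 or use of red blood cell growth factors". The documents do not say whether that dataset holds every component, and not all of its patients were from Duke, so item 3 is the fallback. The strata will be smaller and the benchmark less precise (5/110, for instance, has an exact interval of 1.5% to 10.3%), and the Khorana 1 analysis will have been defined after events were seen.
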